### **Drug Accountability**

The investigational site will maintain accurate records demonstrating dates and amount of study medication received, and accounts of any study medication accidentally or deliberately destroyed.

# STUDY PROCEDURES & TREATMENT PLAN GUIDELINES

# Informed Consent:

A written, signed informed consent form (ICF) and, in the US, written authorization to release and use PHI, will be obtained prior to performing any tests or evaluations under this protocol.

# See Protocol Flowchart (Section 1.0) for detailed timing of tests and evaluations.

### General Concomitant Therapy:

For subjects on any prescription medications, every attempt should be made to keep the patient on a stable dose of that medication for at least 14 days prior to the first dose of study medication and throughout the study

Subjects should advise the investigator if they start taking any new medications, including non-prescribed drugs.

### **Concomitant Psoriasis Therapy**

Patients will be allowed to use the study medication to treat psoriatic skin lesions, if present. The study medication will be applied once daily on areas other than nails, to remain consistent with the prescribing information

Patients will be allowed to use systemic therapy to treat psoriatic lesions. The regimen should be stable for at least 6 months prior to study entry.

# SAFETY PLAN

### **Clinical Safety Assessments**

The following clinical safety assessments will be performed: (See study flowchart)

- Physical examinations
- Vital signs (temperature, heart rate, and blood pressure)
- Monitoring for adverse events
- Monitoring for concomitant therapy

### Laboratory Safety Assessments

The following laboratory tests will be performed at screening:

• Urine pregnancy test, if applicable.

# STUDY FLOWCHART:

Vectical vs. Betamethasone	Screening	Treatment						Follow Up	
	Within 28	Visit 1	2	3	4	5	6	7	8
	Days Prior	W k 1	Wk 4	Wk 8	Wk 12	Wk 16	Wk 20	Wk 24	Wk 28
Test / Evaluation	to Day 1	Day 1	22	50	78	106	134	162	
Informed Consent	х								
Medical History	х								
Physical Exam	Х						х		
Psoriasis Nail Assessment (mNapsi, NAPSI)	х	х	x	х	х	х	х	х	Х
Nail Thickness Measurement	х	х	х	х	х	х	х	х	Х

Vital Signs	х	х	х	х	x	x	х	х	Х
Urine Pregnancy Test 		х						х	
Photography		х	х	х	х	х	х	х	Х
Adverse Events		х	x	х	x	х	х	x	Х
Concomitant Medications	х	x	x	х	x	x	х	x	Х

References:

- 2. Lawry M. Biological therapy and nail psoriasis. Dermatol Ther.20(1):60-7.
- de Jong E, Seegers B, Gulinck M, Boezeman J, van de Kerkhof P. Psoriasis of the nails associated with disability in a large number of patients: results of a recent interview with 1,728 patients. Dermatology. 1996;193(4):300-3.
- 6. Wozel, G. Psoriasis treatment in difficult locations: scalp, nails, and intertriginous areas. Clinics in Dermatology. 2008; 26: 448-59.

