### Additional Objectives

To assess the safety of a 24-week regimen of twice daily Enstilar Foam (calcipotriene and betamethasone dipropionate) in the treatment of nail bed psoriasis.

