### Number of Subjects

Up to 20 eligible subjects will be provided twice daily daily Enstilar Foam (calcipotriene and betamethasone dipropionate). Subjects will be instructed to apply a thin layer on the nail plate, around the nail plate and under the nail plate. The patient will be instructed to apply one application at night immediately before bed and not wash their hands before morning. At week 12, those patients with a mNAPSI50 or less may elect to discontinue study treatment. All subjects who completed the 6-month treatment will be followed for 1 month after discontinuation.

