### Follow-Up Visits

Subjects will return to the investigational site for follow-up visit at 4 weeks after the last study visit.

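### The only physical exam after screening is at Wk 20, four weeks before the end of the 24-week regimen whose safety is to be assessed; moving it to Wk 24 is a minor, nearly free improvement

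*Protocol*

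**What the plan says.** The protocol's Additional Objectives section includes this aim: "To assess the safety of a 24-week regimen of twice daily Enstilar Foam". The Clinical Safety Assessments section names physical examinations first, along with vital signs, adverse events and concomitant therapy, and points to the chart for when they happen: "The following clinical safety assessments will be performed: (See study flowchart". The procedures section does the same: "See Protocol Flowchart (Section 1.0) for detailed timing of tests and evaluations". The flowchart is thus the only place where the exam is timed.

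In the flowchart, the "Physical Exam" row has two marks, at Screening and at Visit 6 (Wk 20, Day 134). It has none at Visit 7 (Wk 24, Day 162) or Visit 8 (Wk 28).

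Three other statements bear on the point:

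- Follow-Up Visits: "Subjects will return to the investigational site for follow-up visit at 4 weeks after the last study visit".
- Number of Subjects, on early stopping: "At week 12, those patients with a mNAPSI50 or less may elect to discontinue study treatment".
- Concomitant Psoriasis Therapy, on use beyond the nails: "Patients will be allowed to use the study medication to treat psoriatic skin lesions, if present".

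**The concern.** With only one exam after screening, its position decides what the exam findings can describe. At Wk 20 it can say nothing about the last four weeks of a regimen whose 24-week safety is an objective. For a subject who stops at week 12, there is no exam between screening and the end of treatment.

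The practical stake is skin away from the nails. Subjects may apply the combined vitamin D and steroid foam to skin lesions once daily. The mNAPSI, NAPSI and nail-thickness measurements do not look at that skin. Of the listed assessments, the physical exam is the one best placed to examine it.

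**Working it through.** No sample-size or power calculation is involved. The check is to read the chart and compare it with the text.

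**Step 1: read the row.** As extracted, the row has ten cells: a label, Screening and Visits 1 to 8. The marks are under Screening and Visit 6. The urine pregnancy test row also has ten cells and puts its second mark under Visit 7 (Wk 24), so a sparse row can resolve to the Wk 24 column.

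**Step 2: identify the end-of-treatment visit.** The regimen is 24 weeks. Follow-up comes 4 weeks after the last study visit, and the chart's last visit is Wk 28. Wk 28 − 4 weeks = Wk 24, so Visit 7 is the last study visit.

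**Step 3: measure the gap for subjects who complete treatment.**

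| Quantity | Arithmetic | Result |
|---|---|---|
| Last exam to Wk 24 visit | 162 − 134 | 28 days |
| Day 1 to last exam | 134 − 1 | 133 days |
| Day 1 to Wk 24 visit | 162 − 1 | 161 days |
| Share elapsed at the exam, by day number | 133 / 161 | 83% |
| Share elapsed at the exam, by week label | 20 / 24 | 83% |

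The chart's day numbers run one week behind its labels: 133 / 7 = 19 weeks and 161 / 7 = 23 weeks. The 28-day gap is the same either way.

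**Step 4: subjects who stop at week 12.** On-treatment exams after screening: 0. If such a subject still attends Wk 20, the exam comes 134 − 78 = 56 days after the Wk 12 visit (Day 78).

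**Step 5: what else is collected.** There are eight post-screening visits. The physical exam is marked at 1 of 8. Vital signs, nail assessments, nail thickness, photography and adverse events are each marked at 8 of 8, including Wk 24 and Wk 28.

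**Step 6: effect of the change.** With the exam at Visit 7, the gap is 162 − 162 = 0 days. No other figure in the protocol changes.

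**The case against.** The strongest reply is that nothing here is stated wrongly. The safety plan promises physical examinations and leaves the timing to the chart, and the chart supplies two. No sentence requires one at the end of treatment. **This stands:** there is no contradiction between the plan and its schedule, and the point is an improvement to a design choice.

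Second, the chart's header starts the Follow Up band at Visit 7, which makes Visit 6 the last column under Treatment. That may well explain where the mark sits. It does not justify it, because the band itself disagrees with a 24-week regimen followed by a visit four weeks later.

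Third, the reading rests on one cell of a table extracted from PDF. The extracted table is in two parts, and the urine pregnancy row used as a check is in the other part. A one-column shift cannot be excluded and would remove the point. The full ten-cell row gives no sign of one, but the original should be looked at before anything is changed.

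Fourth, a Wk 20 exam can still prompt action during treatment, whereas one at Wk 24 comes as treatment ends. This carries little weight, since vital signs and adverse events are already checked at every visit.

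Fifth, adverse event monitoring is not confined to the nails, so reported reactions on treated skin are still captured. **This stands,** and it is the main reason why the loss is small.

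**Conclusion.** The point holds as a minor, cheap improvement. The only post-screening exam falls 28 days before the end-of-treatment visit, and week-12 stoppers have no on-treatment exam after screening. The loss is limited to an exam at the end of exposure, mainly of treated skin. This assumes that the extracted mark is in its true column and that Wk 24 is the end-of-treatment visit.

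A reader might infer more, and the protocol does not support it:

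- **That safety findings will be missed, or that the safety objective cannot be met.** The protocol gives neither the content of the exam nor the number of subjects who will treat skin. No count of missed findings can be derived, and the other safety data continue to Wk 28.
- **That the mark is a copying error.** The chart heading names a different comparison, which suggests reuse of a template. It does not show that this mark was carried over by mistake. The heading is a clerical matter and no part of this point.
- **That the exam row is at fault for loose follow-up after an early stop.** The protocol fixes post-treatment follow-up only for completers: "All subjects who completed the 6-month treatment will be followed for 1 month after discontinuation". Attendance after a week-12 stop is left open, but that gap affects every assessment and is a separate matter.

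**What to change.** First check the mark against the original flowchart. If it is at Visit 6 there too, move it to Visit 7 (Wk 24, Day 162). Add a note that a subject who elects to stop treatment at week 12 has this exam at the Wk 12 visit instead.

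The cost is close to nil: one exam already planned for each subject moves to a visit already scheduled, with no added visit, procedure or subject. The downside is that the Wk 20 exam is lost.
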